5 STUDY INTERVENTION

5.1 STUDY INTERVENTION(S) ADMINISTRATION

5.1.1 STUDY INTERVENTION DESCRIPTION

Whole Health Coaching will be implemented as designed by the VHA OPCC&CT and delivered by a peer specialist who has completed the OPCC&CT Whole Health Coaching training. Whole Health Coaching is explained in detail in the background. Veterans will meet weekly with a peer specialist for 30-50 minutes. The service is designed to accommodate varying patient readiness for change and system barriers, but 8 weeks is a typical length. For this project, the peer support specialist will adjust the time frame and frequency as needed to help Veterans achieve progress on wellness goals. Although typical primary care interventions are briefer, peers in primary care are not bound by the same guidelines typically recommended for PC-MHI providers. Unlike the model for PC-MHI which focuses on facilitating increased access through population-based care (i.e., providing a small amount of services to many patients), the peer support model focuses on improving the patient experience of care. This allows the peers to spend more time with Veterans.

6 STUDY INTERVENTION DISCONTINUATION AND PARTICIPANT DISCONTINUATION/WITHDRAWAL

6.1 INVESTIGATOR DISCONTINUATION/WITHDRAWAL FROM THE STUDY

Participants may be removed at PI discretion for research integrity (e.g., if participants are not completing study expectations such as engaging with the peer support provider) or safety purposes (e.g., if a participant demonstrates elevated risk and would benefit from removal from the study).

6.2 PARTICIPANT DISCONTINUATION/WITHDRAWAL FROM THE STUDY

Participants are free to withdraw from participation in the study at any time upon request.

7 STUDY ASSESSMENTS AND PROCEDURES

7.1 ASSESSMENTS & ASSESSMENT SCHEDULE

Screening Measures. The Blessed Orientation-Memory-Concentration test (BOMC) is a 6-item interview of cognitive impairment that will be administered prior to any other measures. Scores range from 0 (all items correct) to 28 (all items incorrect). This measure has sound psychometric properties. 35 The P4 Screener will be administered by research staff to assess risk for suicide. It assesses the 4 P's: past history, plan, probability, and preventive factors and then classifies respondents as minimal, lower, or higher risk for suicide. The P4 will be re-administered at the follow-up assessments as needed to evaluate risk. The P4 has been validated in several large studies of medical patients enrolled in depression studies and has sound psychometric properties. 36 The PCL-5 will be used to screen for presence of PTSD symptoms. The PCL-5 includes assessment of Criterion A traumatic events. To confirm the absence of non-VA mental healthcare, a short questionnaire titled Non-VA Service Utilization Screen will be administered. Screening for mania, psychosis, non-PC-MHI psychotherapy, and changes to PTSD medications in the past 2 months will be via chart review of VA records and self-report of non-VA services. A Demographics and Military Background questionnaire will be used to assess basic demographic information (e.g. sex, age, education, employment, and income) as well as military background including deployment history (e.g., length, number, and locations), military rank/positions, branch, active/reserve status, and dates of service. This self-report measure is modeled after one used in CIH studies of Veterans with PTSD.

Primary Outcome. The primary outcome directly evaluates the target of Whole Health Coaching: progress toward health and wellness goals. Progress toward health and wellness goals will be measured by Goal Attainment Scaling (GAS), one of the most established applied methods for evaluating individualized progress toward rehabilitation goals. ³⁷⁻⁴⁰ GAS has strong psychometrics as an outcome measure in rehabilitation and mental health. ^{38,40} In rehabilitation, recent reviews show strong inter-rater reliability, convergent validity, and sensitivity as an outcome measure. ^{38,40} In mental health, fewer studies were reported in the review, but available psychometric data are consistent with rehabilitation findings. ⁴⁰ Additionally, GAS demonstrated sensitivity to change in a recent peer-delivered coaching intervention. ⁴¹ GAS is a measurement technique designed to be adapted to meet the needs of individual patients, settings, and studies; we have adapted a version with specified behavioral anchors ⁴² to evaluate the domains targeted by Whole Health Coaching. We selected this version to (1) reduce burden in establishing individualized rating criteria and (2) increase transparency, reproducibility, and validity. We also plan to follow other recommended guidelines to further enhance validity, reproducibility, transparency, and rigor. ³⁹

Secondary Outcomes.

The *Inventory of Psychosocial Functioning (IPF)* consists of 80 items on a 7 point scale measuring functioning in romantic relationships, family relationships, work, friendships and socializing, parenting, education, and self care. ⁴⁹ The IPF was developed to evaluate functional impairment in Veterans with PTSD and demonstrates good reliability, internal consistency, and convergent validity. ⁴⁹

The PTSD Checklist for DSM-5 (PCL-5), a 20-item scale, measures diagnostic criteria of PTSD on a 0-4 scale.50 The PCL-5 demonstrates good reliability and validity.⁵⁰

The 8-item *Client Satisfaction Questionnaire (CSQ)* is designed to measure patient satisfaction with services and demonstrates good reliability.⁵¹

Table 2. Assessment Schedule	Administration Time Points				
Measure	Baseline Assessment	Pre & Follow- up Assessments	Post Assessment	Twice Weekly Assessments (All Phases)	
Blessed Orientation-Memory- Concentration (BOMC)	Х			(
P4 Suicide Screener	Х				
Non-VA Service Utilization Screen	Х				
Demographics & Military Background	Х				
PTSD Checklist-5 (PCL-5)	Х	Х	X		
Inventory of Psychosocial Functioning (IPF)	Х	Х	Х		
Client Satisfaction Questionnaire (CSQ)			Х		
Goal Attainment Scaling (GAS)	X			Х	
*Note. Additional suicide risk evaluations will be conducted as needed to monitor for suicidality.					

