1.2 SCHEMA

2 INTRODUCTION

2.1 BACKGROUND & RATIONALE

[figure not shown]
Veterans with PTSD have high rates of unhealthy behaviors and low rates of positive health and wellness behaviors. Veterans and service members with PTSD have high rates of smoking and substance use, worse health, more sick-call appointments, and low rates of preventative health behaviors (i.e., exercise and medical screening).¹ Veterans with PTSD also have higher rates of inpatient hospitalizations.²,³ Also, despite dissemination of highly effective evidence based psychotherapies for PTSD across VHA,⁴ rates of engagement are low; for example, only 11.5% of Veterans entering treatment with a provider trained in Cognitive Processing Therapy or Prolonged Exposure initiated one of these two treatments, and only 7.9% completed the treatment protocol.⁵ Three classes of interventions demonstrate positive support for increasing "patients' willingness and ability to take independent actions to manage their health and care": (1) skill development, problem solving, and peer support; (2) social environment changes to facilitate healthy beliefs, social norms, and behaviors; and (3) tailored coaching, which facilitates goal setting at appropriate levels.⁶

Whole Health Coaching seeks to increase health and wellness behaviors through a personalized plan for recovery and values-based goal setting. Whole Health Coaching is a health coaching service designed by the VHA OPCC&CT. Whole Health Coaching differs in approach, focus, and principle from

traditional health coaching through defining success in terms of progress on personalized values-based goals rather than disease-specific outcomes. Sessions move through four phases to help Veterans progress on wellness goals. In phase 1, coaches work with Veterans to develop a personal health mission by exploring values and creating a vision for health. In phase 2, coaches conduct assessment to evaluate current and desired functioning in eight areas of self-care and develop a focus. In phase 3, coaches and Veterans develop a plan including setting goals, developing action steps, exploring barriers, and establishing accountability. In phase 4, coaches review progress and modify goals and action steps as needed. Coaches move through phases at the Veteran's pace and can return to a phase at any point as needed.

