Once a focus is selected, Whole Health Coaches help Veterans specify goals, develop action steps to work towards those goals, and evaluate progress. Action steps toward goals might include treatment recommendations or self-care actions from healthcare providers. Coaches also provide support for goal attainment, help Veterans incorporate provider recommendations, and connect Veterans with appropriate services to follow through on action steps. For example, if a goal for a Veteran with PTSD is to reduce hypervigilance or irritability and the Veteran develops action steps towards self-management, then the coach would provide support for the self-management plan. However, if a Veteran with a goal to reduce hypervigilance or irritability develops action steps focused on engaging in formal treatment, then the coach would provide navigation to appropriate services (e.g., PTSD Clinic or anger management) and provide support for maximizing

Table 1. Sample of Whole Health Coaching Assessment and Goals.

Assessment	
Domain	Example
Values	Family and Work
Area of	Power of the Mind:
Focus	Relaxing and Healing
SMART Goal	In the next 3-6 months, I will learn relaxation and mindfulness skills to cope with irritability with my family and co-workers.
Action Steps	In the next week, I will read about VHA treatment options and try a yoga class at the YMCA.

utilization of these services (e.g., developing action steps for attending sessions and completing homework.

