3 STUDY DESIGN

This is a quantitative project with a minor qualitative component. This project will use a multiplebaseline design across participants with non-concurrent replications to measure the impact of Whole Health Coaching on Veterans' progress toward health and wellness goals. In this design, outcomes are monitored over time prior to the onset of an intervention, to establish a baseline, and after the onset of an intervention to evaluate changes in outcomes for each participant.³² In addition, the start of the intervention is staggered across participants to demonstrate experimental control (i.e., that the intervention and not some other extraneous variable was responsible for any changes that were observed). Data from each participant's intervention phase are compared to that person's baseline phase (within-series comparisons) and to the overlapping portions of other participants' baseline phases who have not yet begun the intervention (between-series comparisons). We plan to recruit so that Veterans start baseline in groups of 2-3 and move through the study concurrently. Participants who start baseline concurrently will be randomized to different baseline lengths to establish temporal precedence of change and control for history effects.³² The minimum baseline length of 4 weeks (eight possible assessment points) allows for sufficient assessments for the statistical model. Intervention will be introduced when each participant meets a baseline stability criterion defined as at least four data points total, the final two of which fall within the range of the previous data points (i.e., no increasing slope or trend over the final three baseline data points). There will be flexibility to extend baseline by one week if

participants have not met the stability criterion. The maximum possible baseline will be 13 weeks. Following the baseline period, participants will complete ongoing twice weekly assessments throughout the 8 week peer-delivered Whole Health Coaching phase, and 3-12 week post-intervention phase for the remainder of the 24-week study period.

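### Does the primary outcome change its yardstick when coaching sets or revises a Veteran's goals?

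*Combined protocol and SAP*

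**What the plan says.** Section 7.1 (Primary Outcome) names the construct: "The primary outcome directly evaluates the target of Whole Health Coaching: progress toward health and wellness goals". It introduces GAS in general as "one of the most established applied methods for evaluating individualized progress toward rehabilitation goals". It then turns to the version used here, which has specified behavioral anchors and was adapted "to evaluate the domains targeted by Whole Health Coaching". One stated reason for choosing this version is to lighten the work of building rating criteria person by person; the other is better transparency, reproducibility and validity.

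Table 2 gives GAS a single row, marked at the Baseline Assessment and in the column headed "Twice Weekly Assessments (All Phases".

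Section 2.1 describes the coaching. In its second phase "coaches conduct assessment to evaluate current and desired functioning in eight areas of self-care and develop a focus". Goals come afterwards: "Once a focus is selected, Whole Health Coaches help Veterans specify goals". In its fourth phase "coaches review progress and modify goals and action steps as needed". Section 4 counts setting a goal among the steps of completing the intervention.

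Section 3 states the comparison: "Data from each participant's intervention phase are compared to that person's baseline phase (within-series comparisons". Section 8 analyses GAS by multilevel model and visual inspection, and adds a non-overlap of all pairs effect size.

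**The concern.** Section 7.1 speaks of both goals and domains, and the two differ in when they can exist. The domains of self-care are there before coaching begins. A coaching goal is not: it follows the choice of a focus, is set within the intervention, and may later be revised. The plan does not say in so many words which of the two is rated twice a week, who fixes the content, or what happens to the series when a goal is set or changed.

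This would matter because every planned analysis of GAS needs a common scale. The within-person comparison, the multilevel model, the graphs and the non-overlap index all read a shift between phases as change in the Veteran. If the rated content were replaced during coaching, a shift could come from the replacement. Staggered baselines would not remove this, since goal setting is part of coaching and is staggered along with it. GAS is the sole primary outcome and the only measure in the twice-weekly column of Table 2, so the baseline stability criterion appears to rest on it too.

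**Working it through.** The plan states no figure on this point, so there is nothing to reproduce. The check has two parts: what the text implies about the rated content, and how much of the series would be exposed if that implication were wrong.

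**Reading the sections together**

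1. The phrase about individualized progress describes GAS as a general method. The sentence about this study's instrument describes anchored ratings for the coaching domains, chosen partly to avoid individual criteria. The second governs what is administered.
2. Section 2.1 gives coaching eight areas of self-care. Domains of that kind can be rated on the first day, with no coaching goal in place.
3. Table 2 has GAS at the Baseline Assessment and in all phases, as one row. Section 3 starts coaching only once at least four baseline data points meet the stability criterion. Ratings must therefore exist before any coaching goal does, so a coaching goal cannot be what is rated at baseline.
4. What remains is a switch of content part-way through. The fourth phase of coaching modifies goals and action steps within coaching. No section connects this with the GAS anchors or with the rated content.

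**Exposure if a switch did occur**

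Inputs: 24 weeks in total, baseline of 4 to 13 weeks, coaching of 8 weeks, two ratings a week (section 3).

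- Scheduled ratings: 24 × 2 = 48.
- Baseline ratings: 4 × 2 = 8 to 13 × 2 = 26.
- Coaching ratings: 8 × 2 = 16.
- All baseline-by-coaching pairs: 8 × 16 = 128 to 26 × 16 = 416.

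The session at which a goal is set is not given. Assume weekly session s, from 1 to 5. Coaching ratings after it number 16 − 2(s − 1).

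| Case | Coaching ratings on new content | Pairs mixing content, 4-week baseline | Pairs mixing content, 13-week baseline |
|---|---|---|---|
| Content fixed from baseline | 0 | 0 | 0 |
| Switch at session 1 | 16 | 8 × 16 = 128 | 26 × 16 = 416 |
| Switch at session 5 | 8 | 8 × 8 = 64 | 26 × 8 = 208 |

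The session 1 row is simply every pair there is. By session 5 the count is halved. These counts measure exposure and not bias. They also take 8 weeks of coaching as fixed, whereas section 5.1.1 lets the peer specialist adjust time frame and frequency.

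**The case for a change.** The strongest case for a change is that standardized anchors do not by themselves settle which goal or domain is rated, or that it stays the same. The construct is worded as progress toward goals, and section 7.1 claims reproducibility, yet two teams could in principle build different series from it. The plan to follow further published guidelines on GAS states no rule in this document. As the sole primary outcome, the measure deserves a full definition, and a sentence would cost little.

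Part of this stands. No section says expressly that content and anchors are constant, and none gives a rule for the series when a coaching goal changes. It remains an omission, though, and not evidence that the content moves. A team could reach a different series only by adding a step that the plan does not contain, namely re-anchoring GAS when coaching sets or revises a goal. If the content is fixed at baseline, the comparison is sound on the concern's own terms.

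A stronger remedy, rating re-set goals separately beside a fixed primary series, would not be free. It would need additional ratings of the new goal, in a schedule that already asks for 48 per participant, to deal with a problem that the text does not create.

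**Conclusion.** The concern does not call for a change. The natural reading of section 7.1 with Table 2 is a domain-level yardstick with specified anchors, in use from the Baseline Assessment through all phases. On that reading no pair mixes content, and the phase comparisons in sections 3 and 8 are valid on this point. A sentence confirming constant content would record what the plan already implies. It would not alter the design, the ratings or the analysis.

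The conclusion rests on two assumptions: that the description of the adapted version, and not the general description of GAS, governs what is rated; and that the silence on re-anchoring means none is done. Were the second wrong, between 64 and 416 pairs per participant would be exposed, given goal setting at sessions 1 to 5 and 8 weeks of coaching. The documents give neither the size nor the direction of any resulting bias.

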Multiple procedures will be in place to minimize psychological risk including (1) participants will be reminded that they can choose not to answer any question that they are uncomfortable with, (2) participants will be reminded that they can choose to withdraw from the study at any time, (3) on-call clinicians (licensed independent providers) will be available to speak with Veterans who report distress during any study procedure, and (4) participants will be reminded that they can choose to engage in additional mental health services, including specialty PTSD treatment, at any point in the study. All referral requests will be promptly facilitated by the PI or on-call clinician and urgent requests will be provided with same day access through the facility procedures. This study team has conducted numerous studies using similar methods and there have been very few issues. We do not anticipate any serious or significant risk with these procedures.

A number of procedures will be in place for participants who have more urgent needs including needs for immediate medical or mental health care. If participants should require medical attention, they will

be directed to contact VA medical services, local community hospital, and/or 911 as appropriate. For Veterans who are unable to contact required medical services for themselves, research staff will assist with connecting Veterans with required services. For Veterans who report urgent need of mental health services, they will be evaluated by the on-call clinician and connected with appropriate emergency mental health services as needed. For Veterans deemed at imminent risk of harm to self or others, they will be connected with the on-call clinician who will facilitate emergency services as necessary (e.g., police, Suicide Prevention Team, etc.). The PI and co-Is are licensed clinical psychologists with experience in crisis evaluation and management, and research staff will also have access to a list of on-call clinicians to contact for the study including other licensed psychologists and social workers at the Center. Research staff will have detailed training in these protocols for managing urgent needs including imminent suicidal/homicidal risk. If Veterans enrolled in the study demonstrate non-imminent suicide risk (e.g., ongoing ideation with no plan or intent), additional suicide risk assessments will be conducted by study staff and the intervention provider as needed.

Potential Benefits.

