At risk for suicide	Measured by the P4 screener, defined as any Veteran with "higher" risk on the P4 Screener or Veterans with "lower" risk on the P4 and evaluated by the PI or another clinician to be clinically unstable or at risk. UNTIL Referral to suicide prevention is complete AND connected with ongoing services from a licensed independent provider who agrees to monitor safety concerns, be a point of contact for the peer support specialist, and determines the Veteran is stable for enrollment. Given subsequent eligibility requirement that the Veteran not be receiving psychotherapy in a non-primary care setting, if a Veteran is to be enrolled in the study with LIP monitoring, the LIP would need to be a primary care staff member, ongoing psychiatrist (for medication management only), or PCMHI provider.		
Engaged in psychotherapy in a non- primary care setting in the last 2 months	EMR data (either through datapull or chart review) and self-report		
Changes to psychotropic medications for PTSD within the last 2 months	EMR data (either through datapull or chart review) and self-report		
Preference for direct referral to specialty mental healthcare	Veteran self-report		

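### Psychotherapy outside primary care and PTSD medication changes are checked only at screening; no repeat is planned, although coaching starts 4-13 weeks later and new mental health care is allowed throughout

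*Combined protocol and SAP*

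**What the plan says.** Section 4.1 lists two exclusions with the same look-back: "Engaged in psychotherapy in a non- primary care setting in the last 2 months" and "Changes to psychotropic medications for PTSD within the last 2 months". Both are determined from the medical record and self-report.

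Section 7.1 puts these checks under screening measures. The review of psychotherapy and "changes to PTSD medications in the past 2 months will be via chart review of VA records and self-report of non-VA services". It adds: "To confirm the absence of non-VA mental healthcare, a short questionnaire titled Non-VA Service Utilization Screen will be administered". Table 2 gives that questionnaire, listed as "Non-VA Service Utilization Screen", one mark, in the Baseline Assessment column. The Pre, Follow-up, Post and twice-weekly columns hold only PCL-5, IPF, CSQ and GAS. The only other reassessment described during the study concerns suicide risk.

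Section 3 sets a baseline of 4 to 13 weeks before coaching, 8 weeks of coaching, and 3 to 12 weeks afterwards, for 24 weeks in all. It says that staggered starts are meant to show that "the intervention and not some other extraneous variable was responsible" for observed change.

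Section 2.2 says participants will be reminded that "they can choose to engage in additional mental health services, including specialty PTSD treatment, at any point in the study". Section 2.1 presents engagement in evidence-based PTSD treatment as an ideal element of a Veteran's plan. Section 8 has no rule for concurrent care.

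**The concern.** The entry check describes the 2 months before screening, but the comparison that matters is centred on the start of coaching, weeks later. In between, a participant may begin specialty PTSD treatment, or have a medication changed, and nothing in the planned data collection would record it. Care outside the VA is the most exposed, because it would not be in the VA record either.

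Randomized, staggered baselines guard against events that affect everyone at the same calendar time. They do not guard against one Veteran's own new treatment that happens to begin close to that Veteran's coaching start. With 8-10 completers as the target, individual histories carry weight. At stake is whether the attribution claimed in section 3 can be tested, and whether the pre-post effect sizes that section 8 intends for later power calculations are mixed with the effects of other care.

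**Working it through.** **1. Phase lengths (section 3).** The stated total reproduces at both extremes:

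- shortest baseline: 4 + 8 + 12 = 24 weeks
- longest baseline: 13 + 8 + 3 = 24 weeks

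So the interval from entry to coaching is 4-13 weeks. The completer definition in section 4 allows coaching to begin up to 2 weeks after its scheduled date. If that comes on top, the upper end is 13 + 2 = 15 weeks.

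**2. Share of the 2 months before coaching that the entry check does not cover.** Let w be the look-back in weeks and b the baseline length. Two months is taken as 8 to 8.9 weeks (56 to 62 days). The uncovered share is min(b, w) / w. This assumes that the baseline phase begins on the day of the eligibility check; a gap between the two would enlarge the share.

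- b = 4: 4 / 8.9 = 45% to 4 / 8 = 50%
- b = 9: 100%, since 9 exceeds w
- b = 13: 100%

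**3. Coverage after entry.** Going through the columns of Table 2, none of the 24 weeks is covered by a scheduled measure of other care. Table 2 has no row for chart review even at baseline, so its silence on charts proves nothing by itself. The conclusion about charts rests on section 7.1 placing the review under screening and on no other section describing a second one.

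**4. How likely is any new care among completers?** The documents give no uptake rate, so the rates p below are assumptions. For n completers acting independently, the chance that at least one starts new care is 1 - (1 - p)^n:

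| Assumed p | n = 8 | n = 10 |
|---|---|---|
| 5% | 34% | 40% |
| 10% | 57% | 65% |
| 20% | 83% | 89% |
| 30% | 94% | 97% |

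For example, 1 - 0.9^8 = 0.57. This is the chance that the problem arises at all. It is not the size of a bias.

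**5. What the stability criterion covers.** Under section 3, coaching starts once there are at least four baseline points and the last two lie within the range of the earlier ones, without a rising trend. Three cases follow:

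- Care started in baseline that has already improved GAS should show as a trend, or as a raised baseline level that shrinks the coaching contrast.
- Care started late in baseline, or slow to act, leaves the criterion satisfied. Its benefit then appears during coaching and enlarges the contrast.
- PCL-5 and IPF are not rated twice weekly and no stability rule applies to them. Section 8 gives them descriptive summaries and pre-post effect sizes only.

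**The case against.** The strongest reply has four parts.

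**Purpose.** A reader might infer that the two exclusions exist so that later change can be credited to coaching, and that a lapsed look-back therefore breaks the plan's own rule. No section says so. The synopsis and section 2.1 describe the target group as Veterans not using specialty mental health care, and the psychotherapy criterion can be read as defining that population. The medication criterion fits a stability reading better, but that too is inference. This part stands: no stated rule is broken.

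**Mediation.** Care taken up after coaching begins may be what coaching is meant to bring about; section 2.1 describes coaches helping Veterans reach the PTSD clinic. Dropping every GAS rating after any new care could delete the intervention's successes. This stands for care started after onset. It cannot apply to care started before, and without dates the two cannot be told apart.

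**Detectability.** A reader might infer that the trial would be blind to the problem. That goes too far. Section 8 plans participant-level graphs, so one or two people driving the result would be visible, though not the reason. Referral requests pass through the investigator or an on-call clinician, and VA care could be read from the record later. Still, no such collection is planned, and care outside the VA would be missed.

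**Size.** A reader might infer that a few participants could supply much of the mean effect. If 1, 2 or 3 of 9 gained 1 SD from other treatment, the mean would shift by 1/9 = 0.11, 2/9 = 0.22 or 3/9 = 0.33 SD. Both the number of people and the gain are invented, and the sum assumes that the whole gain falls after onset and none is due to coaching. The documents support no such figure.

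**Conclusion.** The gap is real and modest. Psychotherapy outside primary care and PTSD medication changes are checked at screening, and no repeat is scheduled or described. At the start of coaching, between about half and all of the preceding 2 months is unchecked, depending on baseline length. That result needs only the stated phase lengths and the assumption that baseline follows directly on the eligibility check.

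The stability criterion narrows the problem for GAS to care begun late in baseline or with a delayed effect; it does nothing for PCL-5 and IPF. The direction is open: benefit that emerges during coaching inflates the contrast, while benefit already gained in baseline shrinks it. The amount cannot be worked out from the documents.

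Two limits on scope apply. The psychotherapy exclusion covers any engagement outside primary care, not only newly started therapy. The permission in section 2.2 concerns mental health services; the plan does not say whether medication may change after entry. This is a cheap improvement and not a flaw that invalidates the design.

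**What to change.** - In Table 2, repeat the existing non-VA questionnaire at the Pre, Post and Follow-up assessments, together with a VA chart check that records dates of psychotherapy and of PTSD medication changes. This assumes that the Pre assessment falls at the end of baseline; the plan should say so.
- Mark the start dates of new care on the participant graphs already planned in section 8.
- Report uptake before and after coaching onset separately.
- Limit any sensitivity analysis to care started before coaching onset, for example the multilevel model refitted without those participants. Describe care started after onset without adjusting for it, because it may be part of the intended effect.

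The cost is a few minutes at visits that section 7.2 shows already take place, plus a repeat chart check. The drawback is that the sensitivity analysis would rest on even fewer people than the 8-10 completers. The synopsis dates the study to 2018-2019; if visits are over, a dated chart review could still recover the VA part. None of this alters the care that participants may receive.
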